Certain efficacy variables are not measured at baseline. The MCGI Subject and Rater scales are each sub-divided into two components.

Effective: 24-Dec-2014

Page 11 of 29

Change 12

Section 6.11 Tertiary/Exploratory Endpoints

The text in bold was amended for Retention Analysis (Time to Removal from Study Treatment):

Time to removal from study treatment is defined as the last study day on which the subject received treatment. A completer for the purpose of this analysis is defined as a subject receiving at least 1 dose on Day 7 and the having the SOWS assessment completed. This will be based on the flag indicating the subject completed the double-blind phase as recorded on the CRF. The time to removal from study treatment for completers will be censored on Day 7. The time to removal from study treatment for subjects who complete some treatment on Day 7 but who do not satisfy the definition of completer will be Day 7, uncensored.

This endpoint will be summarized descriptively for each combination of treatment group and gender with Kaplan-Meier curves and tabulations of the number and percentage of subjects newly removed from receiving study treatment on each of study Days 1 to 7. Each Lofexidine dose group will be compared inferentially to placebo with a Cox proportional hazards regression model of time to removal from study, including covariates for treatment and sex. If the Cox proportional hazards model does not converge, then the covariate sex will be dropped from the model and the Cox proportional hazards regression model will be stratified by sex instead. The estimated hazards ratio will be reported as a descriptive measure along with the associated 95% confidence interval.

Justification

To make the definition clearer of what constitutes a completer for this analysis and to redefine the censoring algorithm accordingly. The primary analysis no longer includes site in the model; therefore site has been removed as a variable from all subsequent statistical models.

Change 13

Section 6.11 Tertiary/Exploratory Endpoints

The text in bold was added.

Concomitant Medication Analysis

Effective: 24-Dec-2014

Page 12 of 29

For each of Days 1 to 7, each subject's number of concomitant medication taken will be treated as a continuous variable. Descriptive statistics will be provided on the as-observed data on each study day and also overall study days.

Only days when the patient was taking active treatment will be considered. Days after active administration will be disregarded.

For the calculation of the daily number of medications taken, the number of distinct coded drug names via the WHO dictionary will be used rather than verbatim terms.

Justification

To make the definitions within this analysis clearer.

Change 14

Section 6.13 Safety analysis

Add the text in bold

All subjects who receive at least dose one of study medication will be included in the analysis of safety.

Safety measures will be summarized for the following subject cohorts for the open label phase:

- \neq All treated subjects;
- ≠ Treated subjects without urinary evidence of illicit drug use (i.e. any positive result in the urine drug screen during the open-label phase, including all categories); and
- ≠ Treated subjects with urinary evidence of illicit drug use (may be further subdivided by type of illicit drug used).

Safety measures will only be summarized for all treated subjects for the double blind phase.

Extent of exposure

Extent of exposure will be described by whether the subject took the trial medication and the number of days exposure to double-blind study medication (last date of double-blind medication minus first date of double-blind medication + 1). Average daily dose of double-blind study

Effective: 24-Dec-2014

Page 13 of 29

medication will also be calculated **by number of doses/exposure (days)**. Exposure to open-label medication will also be calculated as last date of open-label medication – first date of open-label medication + 1. No allowance will be made for breaks in therapy in the exposure calculations. Average daily dose of open-label study medication will also be calculated. If the date of last dosing is completely missing for the trial medication then the date of last dosing will be taken for analysis purposes as the date the medication was last dispensed. As there are no open-label dosing dates recorded on the eCRF, dates of visits will be used instead. In particular it will be assumed that open-label dosing starts one day after double-blind dosing ceases.

Justification

To make the definitions clearer.

Change 15

Section 6.13 Safety analysis

Vital Signs During the Double-Blind Phase

The following text was amended:

Vital signs (blood pressure and pulse [sitting or recumbent and standing], respiration, and temperature) will be measured at screening, baseline and before each dose and 3.5 hours after each dose (with the exception of the dose taken at 11 PM, where the measurement at 3.5 hours post-dose will not be done) during the double-blind phase. Summary statistics for observed and changes from screening will be tabulated at each follow-up for each vital sign parameter and at post-baseline double-blind endpoint for each variable.

In addition the number and proportion of subjects having:

- \neq Systolic blood pressure \geq 180mmHg and an increase of \geq 20mmHg from baseline
- \neq Systolic blood pressure \leq 90mmHg and a decrease \geq 20mmHg from baseline
- \neq Diastolic blood pressure \geq 105mmHg and an increase \geq 15mmHg from baseline
- \neq Diastolic blood pressure \leq 50mmHg and a decrease \geq 15mmHg from baseline

will be summarized at each follow-up visits.

The text in bold was added to the following:

Effective: 24-Dec-2014

Page 14 of 29

Vital signs (blood pressure and pulse [sitting or recumbent and standing], respiration, and temperature) will be measured at screening, baseline and before each dose and 3.5 hours after each dose (with the exception of the dose taken at 11 PM, where the measurement at 3.5 hours post-dose will not be done) during the double-blind phase. Summary statistics for observed and changes from **screening** will be tabulated at each follow-up for each vital sign parameter and at post-baseline double-blind endpoint for each variable.

In addition the number and proportion of subjects having:

- ≠ Systolic blood pressure \ge 180 mmHg and an increase of \ge 20 mmHg from screening
- ≠ Systolic blood pressure \leq 90 mmHg and a decrease \geq 20 mmHg from screening
- \neq Diastolic blood pressure \geq 105 mmHg and an increase \geq 15 mmHg from screening
- \neq Diastolic blood pressure \leq 50 mmHg and a decrease \geq 15 mmHg from screening

will be summarized at each follow-up visits.

REFERENCES

Little, RJA and DB Rubin. Statistical analysis with missing data. Version 2. John Wiley & Sons; New York: 2002

Effective: 24-Dec-2014

Page 15 of 29

Protocol Number USWM-LX1-3003-1 Statistical Analysis Plan Addendum 1 Version: Final Issue Date: 24-Dec-2014

Effective: 24-Dec-2014

Page 16 of 29

Protocol Number USWM-LX1-3003-1 Statistical Analysis Plan Addendum 1 Version: Final Issue Date: 24-Dec-2014

Effective: 24-Dec-2014

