6.9.1 Principal Analysis

A pattern-mixture approach⁵, with subjects stratified by disposition within Days 1-7, will be used in assessing SOWS-Gossop AUC (1-7). The 4 disposition strata are as follows:

- Subjects who complete Days 1-7 of the study (i.e. receives at least one dose of study medication on Day 7 and completes the 3.5-hour post-dose SOWS-Gossop assessment on Day 7);
- Subjects who discontinue due to lack of efficacy (including adverse events related to opioid withdrawal);
- Subjects who discontinue due to adverse events related to intolerability or toxicity to study drug; and
- Subjects who discontinue for other reasons.

The inference is comprised of several steps. The first two rely on standard statistical software and a commonly-used type of statistical model. The remaining three rely on matrix manipulations. Additionally, the last step appeals to the statistical delta method (propagation of errors).

- 1. Transformation. Because of the inherent skewness in the SOWS-Gossop scores the raw data will first be transformed to the natural logarithm of the score plus 1.0.
- 2. Modelling. A linear mixed effects repeated-measures model will be constructed for the SOWS-Gossop score. The fixed effects will be disposition stratum, treatment and time, and their respective two-way and three-way interactions, as well as a main effect of gender (randomization stratification factor) and baseline (pre-dose) SOWS-Gossop score as a one degree of freedom covariate. For each combination of treatment and stratum, the time course will be modelled as a linear change point model, allowing for one slope between Days 1 and 2 and a possibly different slope from Days 2 through 7. The model will parameterized to ensure that the predictions from the two line segments agree at Day 2. Subjects will be treated as a random effect, and the slope and intercept parameters will be treated as random coefficients. Modelling the time course, rather than using each time point as a discrete level of a model factor, allows estimation of group means through Day 7 even in the non-completer strata. The choice of Day 2 as the change point is based on prior lofexidine studies, in which SOWS-Gossop mean scores in the placebo group increased from Day 1 to Day 2 and then decreased through Day 7. The modelling allows a different time course for each of the lofexidine dose groups.

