It will be assumed that subjects randomized to lofexidine who withdraw from the study will have a time trajectory comparable to placebo post withdrawal. The pattern-mixture model will be implemented using multiple imputations (Ratitch⁶, 2011). The imputation of missing values and the analysis will be performed multiple times (20 imputed datasets) with the initial seed value set at '123', and the inference of this sensitivity analysis will be based on the combined estimates using the standard multiple imputation technique. This method is detailed in the section entitled "Pattern-Mixture Model with Control-Based Pattern Imputation" (Ratitch⁷, 2013). Briefly, the initial step is to impute the relatively rare, non-monotone missing data via the MCMC Option of SAS® PROC MI. This step uses iterative methods, with which non-convergence is a possibility; should an MCMC imputations that converge will be used in the analysis. This imputation model will be implemented for each combination of gender and treatment. (It should be noted that by performing the imputation for each such combination, the imputation modelling will be richer than the model used to inferentially analyse the data. It is acceptable, even preferable, for the imputation model to be richer than for the analysis model (see Little and Rubin, 2002).

The next step applies to the monotone missing data. The values for each pattern will be imputed using the chained equation method by SAS® PROC MI option MONOTONE REG. This MNAR imputation employs only the appropriate data for each pattern. That is, the missing data for lofexidine treatment arm at time t will be imputed using only the data on placebo subjects up to time t and the data for lofexidine subjects who have data up to time t-1 but are missing data at time t. The model for imputing missing data at time t will include fixed effect terms for study day from the baseline visit through to the t-1 visit and sex. Note that a term for treatment group is not included in this imputed data sets will be analyzed using the MMRM model described below and then summarized using PROC MIANALYZE. The model will include fixed effects for treatment group, baseline log_e (SOWS-Gossop score +1), sex, study day (days 1-7), and

Effective: 24-Dec-2014

Page 7 of 29

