treatment group-by-day interaction. In this model the treatment group term in the model represents the effect of treatment over days 1 to 7. An unstructured covariance model will be used. However, in the event that this model does not converge then the following covariance models will be used in order until the model converges: Toeplitz, first-order autoregressive and compound symmetry. Analysis will be performed using PROC MIXED in SAS and the resultant F-tests will be based on Kenward-Roger's adjusted degrees of freedom.

Justification

Fitting an MMRM analysis without the imputation described above would have entailed an assumption that the missing data are missing at random (MAR). The combined process of imputation followed by MMRM does not assume MAR and provides an unbiased estimate of the treatment effect that follows under the assumption that the mechanism by which data are missing not at random (MNAR) is that upon withdrawal from the study, the SOWS-Gossop trajectory of subjects randomized to lofexidine evolves as the trajectory of placebo subjects.

Change 8

Section 6.9.1 Sensitivity Analysis

The text in bold has been edited:

The following sensitivity analyses will be conducted:

- \neq The above analysis will be performed using the per-protocol population.
- ≠ The log_e (SOWS-Gossop score plus 1) from day 1 to day 7 will be analyzed using a MMRM model on the mITT population.

The model will include fixed effects for treatment group, baseline log_e (SOWS-Gossop score plus 1), sex, study day (days 1-7) and treatment group-by-day interaction. In this model the treatment group term in the model represents the effect of treatment over days 1 to 7. An unstructured covariance model will be used. However, in the event that this model does not converge then the following covariance models will be used in order until the model converges: Toeplitz, first-order autoregressive and compound symmetry. Analysis will be performed using PROC MIXED in SAS and the resultant F-tests will be based on Kenward-Roger's adjusted degrees of freedom. This MMRM analysis assumes that the missing data are missing at random (MAR). This analysis provides an unbiased estimate of the treatment effect that would have been observed had all subjects continued

Effective: 24-Dec-2014

Page 8 of 29

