An MMRM model will be used to test for a difference in the log_e (SOWS-Gossop score +1) at each of days 1, 2, 3, 4, 5, 6, and 7 between the 3.2 mg Lofexidine group and placebo and between the 2.4 mg Lofexidine group and placebo. The model will include fixed effects for treatment group, baseline log_e (SOWS-Gossop score +1), sex, visit (day 1, day 2, day 3, day 4, day 5, day 6 and day 7) and treatment-by-visit interaction. An unstructured covariance model will be used. However, in the event that this model does not converge then the following covariance matrix will be used in order until the model converges: Toeplitz, first-order autoregressive and compound symmetry. Analysis will be performed using PROC MIXED in SAS and the resultant F-tests will be based on Kenward-Roger's adjusted degrees of freedom.

Effective: 24-Dec-2014

Page 10 of 29

Justification

The primary analysis no longer includes site in the model; therefore site has been removed as a variable from all subsequent statistical models.

Change 11

Section 6.11 Tertiary/Exploratory Endpoints

Amend the following text related to OOWS-Handelsman, MCGI (Subject and Rater), VAS-E, and COWS

The same methods used for SOWS-Gossop detailed above on days 1, 2, 3, 4, 5, 6, and 7 will be used for OOWS-Handelsman, MCGI (Subject and Rater), VAS-E, and COWS scores on days 1, 2, 3, 4, 5, 6, and 7. Depending on the distribution of these outcomes data transformations maybe used to normalise the data. Any transformation will be specified within the SAP prior to database lock.

The text in bold was added to the following:

The same methods used for SOWS-Gossop detailed above on days 1, 2, 3, 4, 5, 6, and 7 will be used for OOWS-Handelsman, MCGI (Subject [Severity of opiate withdrawal and side effect index separately] and Rater [Severity of illness and side effect index separately], VAS-E, and COWS scores on days 1, 2, 3, 4, 5, 6, and 7, where the baseline covariate will be the baseline value of the endpoint under analysis. The same model will be used for MCGI [Subject and Rater] and VAS-E, except that there will be no baseline covariate as these endpoints do not have a baseline measurement. Depending on the distribution of these outcomes data transformations maybe used to normalise the data. Any transformation will be specified within the SAP prior to database lock.

Justification

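### The MMRMs fit one baseline slope to all seven days, which can bias the missing-at-random sensitivity and daily analyses, in either direction, if that slope changes over days and drop-out is unequal and related to baseline

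*SAP*

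**What the plan says.** The principal MMRM (SAP Addendum 1, Change 7) has "fixed effects for treatment group, baseline log_e (SOWS-Gossop score +1), sex, study day (days 1-7), and" a treatment-by-day interaction. It is fitted after multiple imputation, and its imputation models use baseline as a predictor (Addendum 1, Change 7; Addendum 2, Change 6).

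The missing-at-random (MAR) sensitivity MMRM (Addendum 1, Change 8) has the same terms, "baseline log_e (SOWS-Gossop score plus 1), sex, study day (days 1-7) and treatment group-by-day interaction", but is fitted to the observed, incomplete scores. Of this analysis the SAP says: "This analysis provides an unbiased estimate of the treatment effect that would have been observed had all subjects continued" on treatment to Day 7.

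The daily SOWS-Gossop MMRM (Change 10) is also fitted without imputation. It again has one baseline term, with "visit (day 1, day 2, day 3, day 4, day 5, day 6 and day 7) and treatment-by-visit interaction". Change 11 carries this form to OOWS-Handelsman and COWS, each with its own baseline. For MCGI and VAS-E, "there will be no baseline covariate as these endpoints do not have a baseline measurement".

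The single slope goes back to the SAP of June 2014, where section 6.9.1 specifies "baseline (pre-dose) SOWS-Gossop score as a one degree of freedom covariate". Addendum 2 adds no baseline-by-day term.

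**The concern.** Baseline SOWS-Gossop is scored on the morning of Day 1 before randomisation, and the Day 1 score follows 3.5 hours after the first dose (Protocol 15.2 and 15.4.1). Day 7 comes six days later. It is plausible, though not shown, that baseline predicts Day 1 better than Day 7.

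A model with one slope then uses too steep a slope on late days. In complete data this costs only precision, because randomisation balances baseline. In incomplete data it matters more. The model uses the slope to adjust the arm means of those who stayed to the baseline level of everyone randomised. If those who left differ in baseline, and more left in one arm than the other, the adjustment errs by different amounts in the two arms.

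At stake are the MAR check on the primary result and the late-day treatment differences. The SAP's claim that the MAR analysis is unbiased also needs a correctly specified mean model, and Change 8 does not state that condition.

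**Working it through.** **The plan's own figure.** The only numerical design figure is power for AUC(1-7) (SAP section 2). It serves here as a yardstick, because the documents give no effect size or SD.
- With 225 v 150, SE = √(1/225 + 1/150) = 0.1054 SD. An effect of 0.376 SD gives z = 3.567 and power Φ(3.567 − 1.96) = 94.6%. That effect was solved from the stated 94.6%.
- The other sample sizes then give 92.7, 90.3 and 87.1%, against the stated 92.6, 90.1 and 86.8%.
- For 2.4 mg, at three-fourths of the effect, power is 76.3% alone. Multiplied by 0.946 it is 72.2%, against the stated 72.6%.

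**Inputs.**
- From the documents: model terms, unstructured covariance, 225:225:150 allocation, and the hypothesis that lofexidine improves completion.
- Assumed, because the documents give none: baseline slopes by day, residual correlation, drop-out rates, and how drop-out depends on baseline. Baseline and residual SDs are set to 1. The simulations use two arms and omit sex.

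**Sign of the bias.** Let b be the common slope, β_d the true slope on day d, and s the mean baseline of all randomised minus that of the stayers in an arm. To first order, the bias in lofexidine minus placebo on day d has the sign of (b − β_d) × (s_lofexidine − s_placebo). Take slopes falling linearly from 0.6 to 0.1, so b = 0.35 and b − β_7 = +0.25. If higher-baseline subjects leave, and more leave on placebo, then s_placebo > s_lofexidine and the product is negative, favouring lofexidine. Reversing either factor reverses the sign. If either factor is zero, so is the bias.

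**Size.** Large-sample maximum-likelihood fits (100,000 per arm, unstructured covariance, true effect zero) with the common slope gave the following. Negative values favour lofexidine; units are residual SD.

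| Slope, Day 1 to Day 7 | Who leaves more | Drop-out, placebo v lofexidine | Overall bias | Day 7 bias |
|---|---|---|---|---|
| 0.6 to 0.1 | higher baseline | about 57% v 38% | −0.018 to −0.026 | −0.054 to −0.067 |
| 0.5 to 0.2 | higher baseline | about 57% v 38% | −0.011 to −0.014 | −0.028 to −0.039 |
| 0.6 to 0.1 | lower baseline | about 57% v 38% | +0.019 to +0.025 | +0.052 to +0.070 |
| rising | higher baseline | about 57% v 38% | +0.018 to +0.026 | +0.047 to +0.071 |
| constant, or equal drop-out | – | – | 0 | 0 |
| 0.6 to 0.1 | higher baseline | 34% v 19% | −0.014 | −0.035 |
| 0.6 to 0.1 | higher baseline | 71% v 48% | −0.034 | −0.093 |
| 0.8 to 0 (extreme) | higher baseline | 63% v 32% | −0.064 | −0.172 |

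With baseline-by-day added, bias was at most 0.005 SD overall and 0.008 SD on Day 7 in the main settings (0.007 and 0.012 in the extreme one), which is simulation error. Against 0.376, an overall bias of 0.011 to 0.026 is 3% to 7%. This is a rough comparison, since the bias is in single-day SD and the 0.376 is in SD of the AUC endpoint.

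**Error rates at trial size.** These come from 1,200 null trials of 150 v 225, with slopes 0.6 to 0.1 and higher-baseline drop-out.
- Overall: mean bias −0.0174, SE 0.0901. The shift is 0.193 SE, so the expected one-sided rate is Φ(−1.96 + 0.193) = 3.9%. Simulated: 3.4%, and 2.0% with baseline-by-day.
- Day 7: −0.0511/0.1461 = 0.350 SE, so Φ(−1.61) = 5.4%. Simulated: 6.1%, and 2.3% with the term.
- Simulation SE near 2.5% is √(0.025 × 0.975/1200) = 0.45 points.
- Two-sided at the SAP's 5%: 4.8% overall and 6.8% on Day 7; with the term, 4.5% and 4.8%.
- Lower-baseline drop-out: one-sided 1.5% overall and 0.5% on Day 7.
- Extreme setting: 10.7% and 21.1%; with the term, 2.8% and 2.7%.

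**Precision of the imputed primary.** In complete data, variance inflation = 1 + (β − b)² × Var(baseline)/residual variance, where β is the slope of the contrast concerned.
- Seven-day mean, linear slopes: mean slope 0.35 = b, so inflation is 0%. Curved slopes gave up to 0.9%. Only strongly convex slopes with growing variance gave 8–17%.
- Day 7: (0.10 − 0.35)² = 0.0625, about 6%. With slopes 0.5 to 0.2, (0.20 − 0.35)² = 0.0225, about 2%. Stronger cases reached 16–30% on single days.

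**The case against.** The strongest reply is that the documents fix neither condition on which the direction depends. A reader might infer that the models lean towards lofexidine whenever drop-out is heavier on placebo and related to baseline. That does not follow: a falling slope with lower-baseline drop-out, or a rising slope with higher-baseline drop-out, gives bias of the same size against lofexidine. SAP section 6.9.1 says that prior placebo means rose to Day 2 and then fell, but a trajectory of means says nothing about how each day's score regresses on baseline. Heavier placebo drop-out is the trial's secondary hypothesis, held alongside better symptom relief; the null simulations assume it without symptom benefit. The cardiovascular discontinuation rules (Protocol 13.2.3 and 14.5.2) could add drop-out on lofexidine and shrink or reverse the imbalance. All of this stands.

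The reply also notes that no confirmatory test is affected. That stands too. Change 8 is a sensitivity analysis, beside per-protocol and tipping-point analyses. Change 10 is exploratory and carries no multiplicity adjustment (SAP 6.12).

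A third reply is that the word unbiased sits beside a stated MAR assumption. That does not fully answer the point: drop-out in these simulations is MAR, and the common-slope fit is still biased. An unstructured covariance does not repair the mean model.

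**Conclusion.** The omission is real and current, and the mechanism holds. The MAR sensitivity MMRM and the daily MMRMs can be biased in either direction when the baseline slope changes over days and drop-out is both baseline-related and unequal. Under the assumed falling slope with higher-baseline drop-out, the size is about 0.02–0.03 SD overall and 0.05–0.07 SD on Day 7. The late-day comparisons are therefore the main concern. Slopes, correlations and drop-out patterns are all assumptions, and the table shows how far the answer moves with them.

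Two further readings are not supported. One is that the primary result is biased or the trial's error rate inflated: the primary model is fitted to imputed, complete data, where randomisation balances baseline. The other is that the primary interval is materially widened: in most settings the seven-day contrast loses little or nothing, and single days lose about 2–6% in moderate settings.

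This is a low-priority improvement to sensitivity and exploratory analyses.

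**What to change.** Add a baseline-by-study-day interaction to every MMRM that has a baseline covariate: Changes 7, 8 and 10, and OOWS-Handelsman and COWS under Change 11. MCGI and VAS-E need no change. Take LS means at the overall mean baseline. In Change 8, state that the estimate is unbiased only under MAR with a correctly specified mean model.

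The cost is 7 − 1 = 6 degrees of freedom among about 600 subjects, slightly more model complexity, and a few words in the SAP. No new data are needed. The day-by-day imputation regressions of Change 7 already let the baseline coefficient differ by day, so the change also brings the analysis model into line with them.

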## 15.4 Efficacy Assessment Methods

### 15.4.1 Short Opiate Withdrawal Scale (SOWS-Gossop)

The SOWS-Gossop [16] will be completed by the subject at baseline (before randomization), once daily at 3.5 hours ( $\pm$  10 minutes) after the first dose of study medication on Days 1-7, and once daily before dosing on Days 8-14. Note that at the time of each daily evaluation, subjects should consider their symptoms over the last 24-hour period or since the last time the subject took this test. Also, this scale should be completed before completion of the OOWS-Handelsman, MCGI, VAS-E, and COWS.

The SOWS-Gossop scale assesses subjective symptoms of opioid withdrawal ([Appendix 1](#)). It is a subject-rated scale consisting of 10 items that are scored on a 4-point scale of 0 = none, 1 = mild, 2 = moderate, and 3 = severe (minimum score of 0, maximum score of 30) (see [Table 2](#) below). The overall score will be the simple sum of the 10-item scores. Lower observed values in SOWS-Gossop scores indicate a more positive clinical outcome.

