### 15.4.3 Modified Clinical Global Impressions Scale (MCGI)

The Clinical Global Impressions rating scale (1985) was developed by the National Institute of Mental Health (NIMH), and originally contained 3 questions. For this study, Questions #1 and #3 have been modified from the original scale, and Question #2 was not included ([Appendix 3](#)).

In the original scale, Question #1 (severity of illness) evaluates the subject using a severity scale from 0 (not assessed), 1 (normal, not at all ill) to 7 (among the most extremely ill subjects). The language of this question has been modified in this study for the subject assessment to make the scale more appropriate to opioid withdrawal. The original Question #2 referred to “global improvement” and is omitted from this study, since all subjects will be treated, and there is no untreated screen withdrawal. Question #3 (efficacy index) records responses on a factorial grid – side effects on one side and therapeutic effects on the other side. Since there is no untreated screen withdrawal data, the therapeutic effect cannot be assessed; therefore, only the side effect responses will be examined.

The MCGI scale is used to estimate the overall clinical benefit of lofexidine treatment. The MCGI will be completed once daily at 3.5 hours after the first dose of study medication on Days 1-7 (after completion of the SOWS-Gossop), and once daily before dosing on Days 8-14 (after completion of the SOWS-Gossop). The modified subject and observer scales used in this study are presented below in [Table 4](#). Lower observed values in MCGI scores indicate a more positive clinical outcome.

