#### 15.4.5 Clinical Opiate Withdrawal Scale (COWS)

The COWS [20] will be used to assess the effectiveness of lofexidine in alleviation of opioid withdrawal, and will be completed during screening, at baseline (before randomization), once daily at 3.5 hours after the first dose of study medication on Days 1-7 (after completion of the SOWS-Gossop), and once daily before dosing on Days 8-14 (after completion of the SOWS-Gossop). The COWS is a clinician-administered instrument that rates 11 common opioid withdrawal signs and symptoms ([Appendix 5](#)). These include: resting pulse rate; sweating; restlessness; pupil size; bone or joint aches; runny nose or tearing; gastrointestinal (GI) upset; tremor; yawning; anxiety or irritability; and gooseflesh skin. The score for each item reflects the severity of the sign or symptom, and the total scores are grouped as mild (5-12 points), moderate (13-24 points), moderately severe (25-36 points), and severe (>36 points).

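### The two MCGI severity models omit a baseline covariate although baseline SOWS-Gossop and COWS are collected; adding one is nearly free and may narrow the intervals

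*SAP*

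**What the plan says.** SAP Section 6.11, as amended by Addendum 1, Change 11, analyses OOWS-Handelsman, MCGI, VAS-E and COWS on Days 1 to 7 with the MMRM used for daily SOWS-Gossop. The general rule on adjustment is: "where the baseline covariate will be the baseline value of the endpoint under analysis". For MCGI (Subject and Rater) and VAS-E the rule is lifted: "there will be no baseline covariate as these endpoints do not have a baseline measurement". The justification given for this is one sentence: "Certain efficacy variables are not measured at baseline".

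The same change splits MCGI into four outcomes, a severity item and a side-effect index for each respondent; for the observer scale it reads "Rater [Severity of illness and side effect index separately".

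The protocol confirms the timing. MCGI has no pre-dose reading in the double-blind phase: "The MCGI will be completed once daily at 3.5 hours after the first dose of study medication on Days 1-7" (Section 15.4.3). Two other withdrawal scales do have one. SOWS-Gossop "will be completed by the subject at baseline (before randomization") (Section 15.4.1), and COWS "will be completed during screening, at baseline (before randomization), once daily at 3.5 hours after the first dose of study medication on Days 1-7" (Section 15.4.5). Neither the SAP nor its addenda discuss using one of these as the covariate for a scale that lacks its own baseline.

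**The concern.** The stated reason treats a covariate as if it had to be the earlier value of the same scale. It does not. Any variable measured before randomisation that predicts the outcome can be included, and it reduces residual variance in proportion to the squared correlation.

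Two of the outcomes have a natural partner among the collected baselines. MCGI-Subject severity is the subject's own rating of withdrawal symptoms, and so is SOWS-Gossop. MCGI-Rater severity is an observer's rating of illness and COWS is a clinician's rating of withdrawal, which is a looser match. The baseline readings are taken in active withdrawal, since entry requires an OOWS-Handelsman score of at least 2 at Baseline, so they are plausible measures of initial severity.

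What is at stake is the width of the confidence intervals for these two items on Days 1 to 7.

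**Working it through.** **Is there a planned figure to reproduce?** No. The documents give no standard deviation, effect size, power or baseline correlation for MCGI or VAS-E.

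**Which outcomes have a suitable baseline?** Change 11 creates four MCGI outcomes, and VAS-E is a fifth.

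| Outcome | What it rates | Collected baseline of similar content |
|---|---|---|
| MCGI-Subject severity | Withdrawal symptoms, by the subject | SOWS-Gossop |
| MCGI-Rater severity | Illness, by the observer | COWS (looser match) |
| MCGI-Subject side effects | Tolerability | None |
| MCGI-Rater side effects | Tolerability | None |
| VAS-E | How well the drug relieves withdrawal | None |

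The last three describe a response to study drug, so they have no counterpart before dosing.

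**Size of the possible gain.** Inputs:
- planned arm sizes of 225 per lofexidine group and 150 on placebo (Protocol Section 10.2), so 375 subjects in each comparison with placebo;
- rho, the within-arm correlation between the added baseline and the outcome, which is an assumption shown over a range.

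For the comparison on one day:

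- adjusted variance = (1 − rho²) × unadjusted variance
- proportional fall in SE = 1 − √(1 − rho²)

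| Assumed rho | 1 − rho² | SE ratio | Fall in SE |
|---|---|---|---|
| 0.1 | 0.99 | 0.995 | 0.5% |
| 0.2 | 0.96 | 0.980 | 2.0% |
| 0.3 | 0.91 | 0.954 | 4.6% |
| 0.4 | 0.84 | 0.917 | 8.3% |
| 0.5 | 0.75 | 0.866 | 13.4% |
| 0.6 | 0.64 | 0.800 | 20.0% |

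**Cost if the covariate is useless.** With rho = 0 and one degree of freedom spent, taking 375 − 4 = 371 residual degrees of freedom, the SE is multiplied by √(1 + 1/371) = 1.0013, a rise of about 0.1%.

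The formula is a single-day approximation with one common rho. It ignores missing data and any change in rho over the week. If rho declines after Day 1, the gain shrinks with it.

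**The case against.** The case for leaving the text alone is substantial. The SAP's rule is coherent and pre-specified: a scale uses its own baseline where it has one, and none otherwise. The protocol's model for the daily scores (Section 17.2.8.3, extended to these scales by 17.2.8.4) listed no baseline covariate, so nothing is contradicted. Omitting a covariate does not bias a randomised comparison. The endpoints are tertiary and tested without multiplicity adjustment. At rho of 0.2 or less the gain is 2% or less. All of this stands, and it limits the point to an optional efficiency gain.

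A reader might go further in several ways that the documents do not support.

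- *That all the exempted outcomes share a construct with SOWS-Gossop or COWS.* VAS-E rates perceived effectiveness of the drug (Protocol Section 15.4.4) and the side-effect indices rate tolerability. Nothing in the documents suggests a useful rho for these three.
- *That the plan's 72.6% power for 2.4 mg can be turned into a power gain.* That figure is for SOWS-Gossop AUC(1-7), not for MCGI on a given day, and it allows for sequential testing. Working back from 94.6% for 3.2 mg, the non-centrality is 1.960 + 1.607 = 3.567. Three-fourths of it is 2.675, so the power of the 2.4 mg test alone is Φ(2.675 − 1.960) ≈ 76%. Multiplying by 0.946 gives about 72.2%, close to the stated figure, so 72.6% is roughly the chance that both tests succeed. It also came from the random coefficients model planned for the study, which as now written already contains baseline SOWS-Gossop (Section 17.2.8.1).
- *That leaving out baseline severity undermines the missing-at-random assumption.* The unstructured MMRM already conditions on each subject's earlier scores on the same scale from Day 1. The documents do not show what a baseline from another scale would add, or that baseline severity drives drop-out.
- *That MCGI and VAS-E are thereby made incomparable with the other scales.* Those scales share no common baseline; each adjusts for its own.

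**Conclusion.** The point holds for two of the five exempted outcomes: MCGI-Subject severity of withdrawal and, with a looser match, MCGI-Rater severity of illness. For these, the absence of an own-scale baseline is not a sufficient reason to adjust for nothing.

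The gain is conditional on a correlation that the documents do not report, so a real loss of precision is possible but not demonstrated. The balance still favours adding the covariate, because the most it is expected to cost is about 0.1% of the SE, while a moderate correlation of 0.3 to 0.5 would return about 5% to 13%. No conclusion on the primary or secondary endpoints depends on it. Label: free improvement.

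**What to change.** In Section 6.11 as amended by Addendum 1, Change 11, replace the sentence exempting MCGI and VAS-E with:

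> For MCGI-Subject severity of opiate withdrawal the covariate is baseline log_e(SOWS-Gossop+1); for MCGI-Rater severity of illness it is baseline COWS; VAS-E and the two MCGI side-effect indices have no baseline covariate.

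Keep treatment, sex, day and treatment-by-day as they are. The covariates should be named item by item, because a sentence covering MCGI as a whole would also put baseline withdrawal severity into the side-effect models, for which there is no rationale. The change should be fixed before unblinding so that the covariate is not chosen after seeing results.

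Cost: one SAP sentence, no new data, and one degree of freedom in each of the two models.
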